## II. Purpose

We propose to seek to recruit participants to be randomized to low versus high (10,000 IU/day) or low versus moderate (4,000 IU/day) dose vitamin D and pool these populations for our primary analyses. The study will focus on health care workers and other individuals from Chicagoland communities with elevated risk of exposure to COVID-19. In addition to their high exposure rates to COVID-19, focusing on health care workers is also useful because they have high rates of vitamin D deficiency due to indoor work and long hours, are likely to tolerate high doses of vitamin D given their generally good health, and have ready access to monitoring for dose toxicity. In addition to HCWs, we have decided to expand our focus to include other adults in Chicagoland communities. Due to vaccine distribution in the coming months prioritizing HCWs, we want to offer the potential benefits of vitamin D in COVID-19 prevention to those who will not have prioritized access to vaccines, or choose to be vaccinated at present. **Thus, our overall aim is to compare the risks of COVID-19 in health care workers and other Chicagoland adults at increased risk of COVID-19 randomized to low (400 IU/day) vs. moderate (4,000 IU/day) or high (10,000 IU/day) dose vitamin D. Our specific aims are:**

**Aim 1:** To compare the risk of developing COVID-19 in health care workers and other Chicagoland community members at increased risk of COVID-19 randomized to low vs. moderate or high dose vitamin D. We hypothesize that moderate and high dose therapy will reduce rates of COVID-19 compared to low dose therapy because vitamin D will reduce symptomatic infection that prompts testing for COVID-19. Our primary analysis will pool subjects randomized to the moderate or high dose and compare them to low dose subjects, with secondary analyses comparing low to moderate and low to high. The design thus seeks to maximize potential to find statistically significant results between different dosages given uncertainty in subject willingness to be randomized to different doses.

**Aim 2:** To compare COVID-19 seroconversion in health care workers and other Chicagoland community members at increased risk of COVID-19 randomized to low vs. moderate or high dose vitamin D. As we suspect the main effect of vitamin D may be to decrease symptomatic disease we hypothesize that there may be little or no difference in seroconversion.

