### Procedures and Materials

Blood labs will be taken from subjects at intake, 3 months, 6 months and, if in the 9-month cohort, 9 months. If subjects are in the 2023 cohort (defined as recruited on or after January 1, 2023) blood labs will be taken from

subjects at intake, 3 months, and, if they are recruited in January or February 2023, they will have one final blood draw in June 2023. Labs for UCM subjects will be drawn at DCAM phlebotomy, River East phlebotomy, or Ingalls Hospital, depending on the location most convenient for the subject. Labs for Rush subjects will be drawn by [name] at his Rush lab.

Intake labs will measure baseline calcium and PTH levels, presence of COVID-19 antibodies, baseline vitamin D levels, and vitamin A levels. Where possible given constraints related to sample storage, analysis and available funding for free vitamin D measurement, vitamin D measurements will include free vitamin D levels measured by ELISA assay, as well as total vitamin D levels.

For Aim 7, Intake labs for UCM subjects will additionally measure vitamin D-binding protein (DBP), RAS components (Renin, Ang II, soluble ACE and ACE2), bradykinin, inflammation markers (IL-6, TNF- $\alpha$ , IL-1 $\beta$  and CRP), and SARS-CoV-2 antibodies against S-protein and N-protein.

Follow-up labs (excluding the final lab) will measure PTH levels, calcium levels, vitamin A levels for those who have high baseline vitamin A, and vitamin D levels for monitoring of the intervention's safety and outcomes, and COVID-19 antibodies for monitoring of the outcome. Records of these levels will be kept by the UCM and RU PIs and laboratories.

Final labs will measure calcium levels, vitamin D levels for monitoring of the intervention's safety and outcomes, and COVID-19 antibodies for monitoring of the outcome. Records of these levels will be kept by the UCM and RU PIs and laboratories. Final labs will not measure PTH levels. During the intervention period, our study monitors PTH levels for active participants, because primary hyperparathyroidism is a risk factor for vitamin D toxicity. Given that participants will no longer be taking study-provided vitamin D after their final lab draw, we do not believe it is medically necessary or an appropriate use of limited study resources to continue checking PTH levels with this final draw.

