Those who enroll in March 2023 will have baseline labs in March 2023 and final labs in June 2023 (3 months later). This is due to the end of study funding in June 2023. This is further specified in Section IV, Table 4 below.

Testing for calcium, PTH, and vitamin D will be done at UCM (UCMC, River East, or Ingalls) or Rush ([name]'s lab), with the site for each subject selected based on which site is most convenient for the subject. Vitamin A, which will be drawn only from UCM subjects, will be sent to an outside lab for analysis. Throughout the study period we will tell subjects about calcium, PTH and vitamin D lab results only if they suggest a safety concern for which we would like them to seek care from a medical professional. Except in the instance of a safety concern, subjects will be blinded to their vitamin A & D levels, calcium and PTH throughout the study to ensure protocol compliance. At the end of their time in the study, we will provide test results to subjects as indicated in "Study Completion Email V4". At the end of the intervention period for all participants in this protocol, we will unblind participants to their vitamin D dose assignment as indicated in "Dose Unblinding Email V1". We will do this at the end of the intervention for all participants because we, as the study team, are also currently blinded to dose assignments until the end of the intervention period for all participants. For participants who transition to participate in protocol 20-0847, unblinding will occur at the end of the intervention period for all participants in that study. Blood draws for COVID-19 antibodies will also occur at same location as their other lab draws for convenience, consolidated with other labs, but antibody testing will occur at UCM using the Roche assay for consistency given the differing ranges of different COVID-19 assays. Subjects will be instructed during the consent process to seek COVID-19 PCR testing on their own at a site convenient for them if they become symptomatic or were exposed to COVID-19, which is aligned with recommendations from CDC and IDPH. COVID-19 PCR tests will not be part of the research labs, and thus will not be paid for by the study. Subjects will self-report positive COVID-19 PCR results in the quarterly survey. Laboratory records will be monitored regularly by site PIs, Co-Investigators, and members of the DSMB and Clinical Advisory Committee for safety. Patient-reported outcome measures will be measured by a RedCap-based survey.

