The intake survey will collect baseline data on subjects' current medications and supplements with doses (e.g., multivitamin, zinc, calcium, vitamin D), average time outside per day (specifying direct vs. indirect sun exposure), Fitzpatrick skin type, exercise habits, diet, sleep habits, possible COVID-19 symptoms such as fever, cough, GI problems, and other influenza-like symptoms. Subjects will also be asked to report suspected exposure to the virus (e.g. if a family member falls ill), specific occupation, and demographic information. Subjects will also be asked to evaluate risks of exposure. Participants will also be asked in the intake surveys for the name and contact of information of 1-2 people who could reach them and answer follow-up questions if they cannot be reached or answer questions themselves. Follow-up surveys at months 3, 6, and 9 will ask the participant (or proxy if needed) whether the participant has had a clinically confirmed diagnosis of COVID-19, and the date if so, ask about rates of study medication adherence, and assess for changes in the intake questions about use of other supplements, sun exposure, diet, exercise, and COVID-19 exposures. If the patient is reported to have had COVID-19, we ask about severity, including hospitalization and duration, ICU-use and duration, and need for mechanical ventilation and duration, death and COVID-19 symptom severity using the BEAT-19 adapted to reflect the worst symptomology during their period of active COVID-19. In addition to these questions, we have added some questions on the baseline and follow-up surveys that evaluate additional possible risk factors for COVID-19 outcomes. These risk factors—hypertension, diabetes, and mood—are shown to have possible linkages to vitamin D levels. These factors are receiving increased attention in the context of COVID-19 risk and its relationship to low vitamin D levels. While available evidence suggests there is a link between hypertension/cardiovascular disease, diabetes and metabolism, depression/anxiety, and vitamin D levels, to-date no causal relationship has been established. This is supported by both evidence as recently as this year, as well as earlier studies. Questions about hypertension and diabetes are of our own construction, and questions about depression and anxiety come from validated instruments, the GAD-2 and the PHQ-2. We hope to shed light on the relationship between our outcomes of interest, vitamin D, and these risk factors by asking subjects, both already enrolled and new, about these factors.

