For our primary outcome of COVID-19 infection as measured by patient report of clinically confirmed COVID-19 (or viral PCR when available) and secondary outcomes of COVID-19 antibody seroconversion and disease severity (hospitalization, ICU stay, ventilator use, death), hazard models will be employed to assess the effect of each vitamin D dosing strategy on the outcome. We will first develop hazard ratios for between-group analyses on the primary outcome using log-rank tests, and then develop Cox proportional hazard models to model the hazard function on a set of covariates including but not limited to, moderate or high vitamin D dose, baseline vitamin D levels, age, gender, race, ethnicity, sun exposure, sleep habits, exposure of cohabitants, job type, and study site. We will also control for randomization date to adjust the underlying hazard function for COVID-19 prevalence over time. While our primary analysis will pool subjects randomized to either the moderate or high dose and compare them to low dose subjects, we will also perform secondary analyses comparing low to moderate and low to high and additional analyses that use post randomization vitamin D levels as time varying covariates. The design thus seeks to maximize potential to find statistically significant results between different dosages given uncertainty in subject willingness to be randomized to different doses. As noted above, the sample size was chosen to have at least 80% power to detect a 25% or larger decrease in the hazard of developing COVID-19 between study arms at  $p<0.05$  assuming a 30% baseline 10-month COVID incidence over the study period, in line with the 3% monthly incidence cited above. As finding that a higher dose has no effect or a paradoxical adverse effect on COVID incidence would both lead to use of a lower dose given even the small risks of higher dose vitamin D, Ruxson and Neuhauser would argue for use of a 1-sided test, resulting in 80% power to detect a 20% or larger decrease.

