The proportional hazards assumption will be assessed using the *estat phtest* command in Stata with rejection of proportion hazards defined by  $p<0.05$  for any variable or the global test, or by visual assessment of Schoenfeld residuals. Continuous variables which fail proportional hazards will be categorized. For any categorical variable or categorized continuous variable which fail proportional hazards, we will perform Cox regression which stratifies based on that variable. If moderate or high dose vitamin D variables fail the proportional hazards assumption, we will estimate non-proportional hazards models. Assuming missingness at random, we will impute missing values of covariates with multiple imputation by chained equations with 20 imputations. Covariates in the imputation will include the covariates in the primary analysis excluding moderate or high dose vitamin D variables. Data analysis will be executed in Stata 18.0.

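### Aim 2 seroconversion is known only to fall between quarterly draws, but Section IX names no model form except Cox and gives no event-date, tie or missed-draw rule (minor, secondary endpoint)

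*Combined protocol and SAP*

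**What the plan says.** **How seroconversion is observed.** Section III, Procedures and Materials, sets the schedule: "Blood labs will be taken from subjects at intake, 3 months, 6 months and, if in the 9-month cohort, 9 months". Follow-up and final draws include "COVID-19 antibodies for monitoring of the outcome". The 2023 cohorts differ: "Those who enroll in March 2023 will have baseline labs in March 2023 and final labs in June 2023 (3 months later"), so they have a single follow-up interval. Under Section IV, Table 4, participants enrolled in January or February 2023 have a month-3 draw in April or May and a last draw in June, so their second interval is shorter than their first.

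**How the clinical outcome is observed.** The follow-up surveys ask "whether the participant has had a clinically confirmed diagnosis of COVID-19, and the date if so". The primary outcome therefore has a date of its own between visits; seroconversion does not.

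**How both are to be analysed.** Section IX gives one approach to the primary outcome and to "secondary outcomes of COVID-19 antibody seroconversion and disease severity (hospitalization, ICU stay, ventilator use, death), hazard models will be employed". It describes log-rank tests for the primary outcome and says the team will "then develop Cox proportional hazard models to model the hazard function on a set of covariates". The diagnostics that follow (a Schoenfeld-type test, stratified Cox regression) belong to Cox models. Non-proportional hazards models are provided for only if the dose variables fail the check. The section adds that "Data analysis will be executed in Stata 18.0", but no tie method, event-date rule or missed-draw rule.

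**What Aim 2 expects.** Section II: "we hypothesize that there may be little or no difference in seroconversion".

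**The concern.** The design makes seroconversion times interval-censored. The data say only that conversion fell after the last negative draw and by the first positive one, a window of about three months, longer when a draw is missed and shorter or single in the 2023 cohorts. An analyst who follows Section IX must pick a date for each conversion, and the draw date is the obvious pick. Many events would then share a few nominal times, and the fitted hazard ratio would depend on how ties are broken, which the plan leaves open. Unequal windows and missed draws would also go unrecognised. At stake is a modest amount of accuracy in a secondary hazard ratio, and an analysis choice that could be settled after the data are seen.

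**Working it through.** **1. The plan's own figure.** Inputs: 2,000 participants, half to low dose (Sections VII and VIII); hazard ratio 0.75, 30% low-dose incidence over 10 months, p<0.05 taken as two-sided (Section IX).

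- Expected events: 1,000 × 0.30 + 1,000 × (1 − 0.70^0.75) = 300 + 235 = 535.
- Events needed (Schoenfeld): 4 × (1.960 + 0.842)² / (ln 0.75)² = 31.40 / 0.08276 = 379.4, so 380.
- Power: Φ(√(535/4) × 0.2877 − 1.960) = Φ(1.37) = 91%.

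The stated minimum of 80% holds as a lower bound. It concerns the primary outcome. The plan gives no incidence, effect or power for seroconversion, so the 30% and 0.75 are borrowed below as assumptions.

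**2. Risk per three-month interval** (constant hazard).

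- Low dose: p0 = 1 − 0.70^0.3 = 0.10148.
- Higher dose: p1 = 1 − 0.70^(0.3 × 0.75) = 0.07712.

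**3. What each method tends to if the draw date is the event time**, with common draws at 3, 6 and 9 months.

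- Breslow ties give the ratio of interval risks: p1/p0 = 0.760. On the log scale 0.2745/0.2877 = 0.954, a shrinkage of 4.6%.
- Exact ties give the odds ratio: (0.07712/0.92288) / (0.10148/0.89852) = 0.740, away from 1.
- Efron ties, solved numerically: 0.750.
- Grouped-time proportional hazards (complementary log-log): ln(1 − p1)/ln(1 − p0) = 0.08025/0.10700 = 0.750, the true value.

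With a true hazard ratio of 1, p1 = p0 and every method gives 1.00.

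**4. Range over the assumed incidence** (true hazard ratio 0.75).

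| Low-dose seroconversion | Nine-month total | Breslow | Efron | Exact |
|---|---|---|---|---|
| 1% per month | 8.6% | 0.7528 | 0.7500 | 0.7472 |
| 2% per month | 16.6% | 0.7557 | 0.7500 | 0.7443 |
| 3% per month | 24.0% | 0.7585 | 0.7501 | 0.7414 |
| 30% per 10 months | 27.5% | 0.7599 | 0.7502 | 0.7399 |
| 5% per month | 37.0% | 0.7642 | 0.7503 | 0.7354 |
| 10% per month | 61.3% | 0.7788 | 0.7513 | 0.7196 |

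**5. Size against sampling error.** Expected seroconversions by nine months: 1,000 × (1 − 0.70^0.9) + 1,000 × (1 − 0.70^0.675) = 275 + 214 = 489. The log hazard ratio has a standard error of about 2/√489 = 0.090. The Breslow shift is 0.2877 − 0.2745 = 0.013, about one seventh of that.

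**6. Simulation** (2,000 participants, 30% per 10 months, true hazard ratio 0.75).

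- Fixed draw dates, 500 trials: true event times 0.749, Breslow 0.759, Efron 0.749; rejection 90%, 88% and 90%. With a true hazard ratio of 1, rejection was 5%, 4% and 5%.
- Draw dates spread over one month, 300 trials: true times 0.752, draw dates 0.755 with either tie method. The shift falls from 0.010 to 0.003.
- The same spread with 20% of draws missed equally in both arms, 300 trials: 0.745 against 0.751, a shift of 0.006.

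**The case against.** The strongest reply is that the plan never says the draw date will be the event time. It speaks of hazard models, a term that also covers interval-censored and grouped-time forms, and its log-rank sentence is confined to the primary outcome. That stands: draw-date Cox is an inference from Cox being the only form named, not plan text.

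The reply on size also stands. Draws are drop-in appointments with reminders until completed (Sections IV, VIII and XVII), so dates will vary and ties will be fewer than in step 3. The unequal 2023 intervals follow from enrolment date, which randomisation should balance between arms and which Section IX adjusts for through randomization date. Nothing in the documents suggests that draw timing or attendance differs by arm.

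A reader might infer that the plan builds in a systematic pull towards the no-difference result that Aim 2 expects. The documents do not support this. The pull arises with Breslow ties, is almost absent with Efron on common draw dates, reverses with exact ties, and does not exist at a hazard ratio of 1. A reader might also infer that the Aim 1 and Aim 2 hazard ratios become impossible to compare. No section plans that comparison, and a shift of 0.01 would not prevent it.

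What the reply does not remove is the gap itself: the endpoint is interval-censored by design, and the section that should say how to handle this does not.

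**Conclusion.** The point holds as a minor one on a secondary endpoint. At the plan's borrowed incidence, a draw-date Cox analysis of a true hazard ratio of 0.75 would report between 0.74 and 0.76 depending on an unstated tie option. With Breslow ties the log hazard ratio shrinks by about 4 to 5%. The shift is less than half as large when draw dates vary by a month. It would be larger if seroconversion exceeded 30%, but no higher figure stands in the documents. The primary analysis is unaffected.

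These figures assume a constant hazard, seroconversion as frequent as clinical COVID-19, a perfect assay, no antibody waning, and the same draw schedule and attendance in both arms. Draw timing or attendance that differed by arm could produce a larger bias in either direction; the documents give no sign of it.

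**What to change.** In Section IX, give Aim 2 its own sentence:

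- Define the event interval as running from the last negative draw to the first positive draw, using actual draw dates. Censor participants who never convert at their last negative draw.
- Fit an interval-censored proportional hazards model to these intervals, or a complementary log-log model by draw wave with interval length included. Both target the hazard ratio, and both let missed draws and unequal 2023 intervals enter directly.
- Restrict this analysis to participants antibody-negative at baseline. Section XVII invites back people previously disqualified for a positive baseline antibody test, and they have no last negative draw.
- Replace the Cox-specific proportional hazards check for this endpoint, for example with a dose-by-wave term.

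If Cox is kept for Aim 2, state the event-date rule, the tie method and the missed-draw rule before unblinding. Leave Aim 1 as it is, since it has reported dates. The cost is slightly more analysis work, and no new data.

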#### IV. Probable duration

The study period, including recruitment, enrollment, and analysis, will last 36 months. If we are granted a no-cost extension from our funder, NCATS, we expect the recruitment period to last until March 31, 2023, so one year longer, to enroll our target of 2,000 subjects. Once enrolled, subjects' participation will last up to 21 months total. This includes up to 9 months of taking a daily dose of vitamin D, attending laboratory appointments for testing, and answering surveys, and 12 months of chart review thereafter to measure outcomes.

NCATS has granted us an initial no-cost extension to continue the study through June 30, 2022 and our study timeline according to that funding period is specified in Table 1 and Table 2. Given delays in recruitment due in large part to the changing landscape of COVID risk, more infectious variants, the current flu season, and vaccine rollout, we wish to further extend our recruitment period through the end of March, 2023 but this is contingent on an additional no-cost extension from NCATS. We have requested an additional no-cost extension through June 30th, 2023 and anticipate hearing back sometime Spring 2022 with an answer. Should we receive this second extension, we will continue the study through June 2023. In this case, we will adapt to the study timeline specified in Table 3 and Table 4, rather than Tables 1 & 2, specified below. In either scenario, some subjects will participate in our study for 9 months, and others for 3-6 months, depending on when they are recruited to the study (see tables for these dates). Based on our understanding of vitamin D levels in the blood over time including seasonal variation, we believe subjects who participate on treatment for 3 to 6 months will achieve appropriate serum vitamin D levels for analysis. We plan to adjust our analyses for this cohort accordingly.

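### Randomization date alone cannot follow COVID-19 waves within follow-up, so the time-varying vitamin D level analysis is open to calendar-time confounding of uncertain direction

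*Combined protocol and SAP*

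**What the plan says.** Section IX (Description of statistical analysis) plans log-rank tests and then Cox models. On changing epidemic risk it says: "We will also control for randomization date to adjust the underlying hazard function for COVID-19 prevalence over time". It states neither the time scale nor the form of the date term (linear, categorical or strata). The covariate list is open-ended and includes "race, ethnicity, sun exposure, sleep habits, exposure of cohabitants, job type, and study site". It names no calendar-time, season or local-incidence term.

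The main comparison is the randomized one: "our primary analysis will pool subjects randomized to either the moderate or high dose and compare them to low dose subjects". Beyond the secondary dose contrasts, the section adds "additional analyses that use post randomization vitamin D levels as time varying covariates".

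Three other places bear on this:
- Section III (Procedures and Materials) sets the draws: "Blood labs will be taken from subjects at intake, 3 months, 6 months and, if in the 9-month cohort, 9 months".
- Section IV (Probable duration) recognizes "vitamin D levels in the blood over time including seasonal variation".
- Section IX has a fallback for non-proportional hazards: "Continuous variables which fail proportional hazards will be categorized", and for a categorical or categorized variable that fails, "we will perform Cox regression which stratifies based on that variable".

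**The concern.** The stated purpose is to let the underlying hazard follow prevalence. The stated tool is a covariate that does not change during a person's follow-up. With staggered entry through March 2023, people at the same month since randomization stand at different points of the epidemic, and a single date effect does not line them up.

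For the dose comparison this matters little, because entry date is independent of arm. Achieved vitamin D level is different: it is not randomized, and it varies with season. If incidence varies over the same calendar, level and risk can be associated when level has no effect. The Background says that the vitamin D needs of immune function are not known, and an achieved-level analysis speaks to that question. A spurious gradient of either sign would mislead.

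**Working it through.** **1. The plan's own figure.** The plan gives no figure for the level analysis. Its power statement concerns the randomized comparison and holds. For HR 0.75 at two-sided 0.05 and 80% power, events needed = 4(1.960 + 0.842)² / (ln 0.75)² = 380. With 1,000 per arm and 30% control incidence, expected events = 1,000 × [0.30 + (1 − 0.70^0.75)] = 535, and power is 91.4%.

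**2. What a date term can do.** Let R be randomization date, t time since randomization, and c = R + t calendar date.
- Log-linear trend: log hazard = βc = βR + βt. The baseline hazard absorbs βt and a linear date term absorbs βR. Adjustment is complete.
- Wave: log hazard = A·cos(c) = A·[cos R·cos t − sin R·sin t], with dates as angles. This is an interaction of R with t. No function of R plus function of t reproduces it, so even month-of-randomization dummies fail as main effects.

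**3. Inputs.**
- From the documents: N = 2,000; 3% monthly incidence; 3 to 9 months of follow-up; quarterly draws. Section VIII reports incidence falling from about 2% to about 1% a month over one summer, and community rates rising from 15 to 70 per 100,000 (70/15 = 4.7-fold).
- Assumed, because the documents give no value: recruitment start (January 2021 in set A), peak-to-trough COVID-19 ratio, seasonal swing in vitamin D, both peak dates, and the dose mix.

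**4. Result with no true effect of level.** Set A is a piecewise-exponential approximation to the Cox model with linear randomization date, arm, baseline level and the last drawn level. Sets B and C are separate checks of the same question. The vitamin D peak is 1 September throughout. Entries are HR per 10 ng/ml; brackets give the two-sided rejection probability at nominal 5%.

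| COVID-19 peak | A: 4:1 wave, ±4 ng/ml | B: 4:1, ±4, all intervention subjects on 4,000 IU | C: 3:1, ±3, all on 4,000 IU |
|---|---|---|---|
| 1 December | 1.06 (21%) | 1.14 | 1.11 |
| 1 January | 1.00 (5%) | 0.99 | 1.01 |
| 1 February | 0.95 (21%) | 0.86 | 0.91 |
| 1 March | 0.91 (50%) | 0.78 | 0.84 |
| Range if half take 10,000 IU | not reported | 1.05 to 0.91 | 1.01 to 0.98 |
| Calendar time scale | 1.00 (5%) | 1.00 | not reported |

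A and B share wave, swing and peak dates, so the gap between them comes from the remaining assumptions, such as the level each dose produces and how much levels vary between people. In set A, month-of-randomization dummies gave 0.927 (34%) for the 1 March peak, against 0.911 with linear date.

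**5. Why the sign changes.** With draws 3 months apart, the level in force is 0 to 3 months old, on average about 1.5. A true peak on 1 September becomes a recorded peak near mid-October. A COVID-19 peak on 1 December is then 1.5 months away: cos(45°) = 0.71, so recorded level and risk move together (false harm). A 1 March peak is 4.5 months away: cos(135°) = −0.71 (false benefit). Set A is consistent with this:
- With an August vitamin D peak, COVID-19 peaks on 1 December, January and February give 0.997, 0.948 and 0.915.
- If the level were current rather than carried forward, peaks from 1 December to 1 February give 0.876 to 0.975, always false benefit.

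**6. The fallback.** It acts only if date fails the proportional-hazards check. In these scenarios a date-by-time test has 12 to 14% power at N = 2,000. If it did trigger, strata by quarter of randomization would move 0.911 to 0.980 and leave ln(0.980)/ln(0.911) = 0.22, about one fifth of the log bias.

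**7. The randomized comparison.** In a simulation of both time scales the treatment HR was 0.755 under each, with the same SE (0.108 with a 3:1 wave, 0.104 with 5:1).

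**The case against.** The strongest reply is that this concerns an exploratory analysis and an under-specified model. The form of the date term is open. A linear term is enough for a log-linear trend. Strata by month of randomization would also work, because within such a stratum time since randomization fixes calendar date to within a month. The covariate list is not closed, and sun exposure and COVID-19 exposures are reassessed at the follow-up surveys. If entered as time-updated covariates they might absorb part of the confounding, which was not modelled. All of this stands. It limits the size and reach of the point, but it does not supply a calendar term, and the fallback is unlikely to.

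A reader might go further and infer a bias toward false benefit, since vitamin D is low and respiratory infection high in winter. Particular assumptions do give that. One simulation of 120 trials with a 3:1 winter-to-summer hazard and a ±3 ng/ml swing gave HR 0.93 and 13% rejection (95% interval about 8 to 21%); 5:1 and ±5 ng/ml gave 0.90 and 30%. The documents do not support the general claim. They give no peak dates or vitamin D amplitude, and Section IV attributes changing risk also to variants and vaccine rollout, which need not follow season. The quarterly lag can cancel or reverse the sign.

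**Conclusion.** The point holds in limited form. On a time-since-randomization scale, which the wording implies but does not state, randomization date as a main effect does not achieve the stated purpose when incidence comes in waves. The time-varying level analysis is therefore open to calendar-time confounding. Over the scenarios examined, the spurious HR per 10 ng/ml ran from about 1.14 to about 0.78. It was close to 1 for some peak dates and for a dose mix with many subjects on 10,000 IU. These figures illustrate a range and are not an estimate for this trial.

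Two stronger readings fail. It is too absolute to say that the date term adjusts for nothing, since it removes a log-linear trend. Nor is the primary result threatened, since date is independent of randomized arm. This is a cheap improvement to an additional analysis.

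**What to change.** In the time-varying vitamin D level model, do one of the following:
- Use calendar date as the time scale with delayed entry at randomization, and keep a term for time since randomization. The term is needed because levels rise after dosing starts and a calendar scale no longer matches on time since randomization.
- Keep time since randomization as the time scale and split follow-up by calendar month, with month as a stratum.

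State the chosen time scale in Section IX, and do not rely on randomization date alone as the adjustment for prevalence in that model. The randomized comparisons may stay as planned; changing their time scale is optional.

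The cost is a little more analysis work, mainly data splitting. It uses dates that the survival analysis already needs and requires no new data.
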